3.0 Inclusion and Exclusion Criteria

- 3.1 Inclusion Criteria: Patients over the age of 18, with continuous enrollment in the Cigna Medicare Advantage health plan in Texas starting July, 2016 until January 2018 with a diagnosis of comorbid DM and HTN and having a prescription filled for an ACEI or ARB medication during the month of January, 2017. The patient identification period will be included in the study. Patients who disenroll or die before the study ends will be excluded from the study.. Exclusion criteria include having a diagnosis (identified by ICD-10 codes) for dementia, or an ACEI/ARBS contraindication like angioedema, hyperkalemia, renal artery stenosis.
- 3.2 Describe how potential subjects will be screened for eligibility based on these criteria: The retrospective analysis will apply these exclusion and inclusion criteria during the data analysis stage to give the final cohort of patients.
- 3.3 This study will not include any vulnerable population, mentioned below:
 1. Adults unable to consent
 2. Individuals who are not yet adults (infants, children, teenagers)
 3. Pregnant women
 4. Prisoners
 5. Students for whom you have direct access to/influence on grades
 6. Economically and/or educationally disadvantaged persons

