9.0 Procedures Involved

9.1 Phase 1: Retrospective data analysis

Patients that used a study medication during January 2017 will be identified and the first prescription date during this time will be considered the index date. A dummy variable will be created to indicate prevalent user vs incident user by evaluating the 6 month data prior to index date (July – December 2016). Patient adherence will be assessed during the one year following the index date.

Adherence will be measured as proportion of days covered (PDC). PDC rates over the entire 360-day assessment period will be determined. PDC will also be calculated separately for each month during the one year following the index date. During each of the 12 consecutive 30-day periods of adherence assessment, a binary indicator for “full adherence” each month, defined as PDC= 0.8 vs. non-adherence will be created. The 12 binary indicators of full adherence will then be modeled during each 30-day period as a longitudinal response in a logistic group-based trajectory model. Patients will be assigned to a trajectory on the basis of these models. Several logistic regression models will then be carried out to identify predictors associated with specific trajectories for adherence.

9.2 Covariates: Demographics (age, gender, and language), physician specialty (primary care vs. specialist), health plan (low income subsidy vs.

A motivational interviewing intervention customized by patient adherence patterns (NCT03985098) – 03.28.2018

other), prevalent vs. incident user, Centers for Medicare and Medicaid CMS Risk Score, Charlson comorbidity index (CCI) and number of distinct medications. Additionally, selected co morbidities will be identified by ICD-10 codes during the one year prior to index date including congestive heart failure, coronary artery disease, peripheral vascular disease, myocardial infarction, diabetes, stroke hypertension, end stage renal disease (ESRD), chronic obstructive pulmonary disease, asthma, and depression. To ensure appropriate risk adjustment in the models, additional covariates which will be added to the model include, regimen complexity, class of antihypertension medication used, baseline adherence measured as PDC, previous hospitalization and patient's trajectory prior to intervention.

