Customization of intervention: After completion of the retrospective analysis phase and identifying the major trajectories in this patient population, the team will meet to discuss the patterns identified, the potential barriers likely to be associated with each trajectory, and strategies that can help patients within each trajectory based on their behavior pattern. The team will then develop customized education specific to each identified trajectory. For example: some patients can have high medication use in the early part of the follow up period but poor after, others may have low initial use and improved subsequent. Some may have intermittent adherence throughout the follow up time, others may simply discontinue. The expected barrier and potential solutions that should be discussed with the patient using MI strategies will vary accordingly. Patients past adherence patterns will guide the team in determining probable barriers and what can potentially help the patient. For example, patients who discontinue the medication may have side effects concerns or may view the medication as unnecessary. Patients who continue to take medication but have less than 0.8 PDC throughout may be forgetting to take the medicine and need help remembering. The team will create a code for each trajectory identified to categorize the patients. A protocol for each trajectory will be developed to summarize the education that is likely to benefit patients with the specific behavior pattern given the code. All the developed protocols will be based on the Ask-Provide-Ask approach, a pharmacist adaptation for the Elicit-Provide-Elicit approach of MI (attached)

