9.3 Phase 2: intervention implementation

Patients that are still enrolled in the health plan during 2017-2018 will be included in phase 2. Patients will be categorized by their adherence trajectory identified in phase 1 and will be randomized to intervention vs. not within each category. The proposed intervention will be a telephone call by a pharmacy student participating in rotations at Cigna-Health Spring Plan and trained in MI and 6 monthly follow up calls. During implementation, students will first examine the patient adherence pattern that was identified in phase 1 which will be coded. The student will then confirm the diagnosis, medication name, and dose with the patient answering the call and will follow the outlined protocol. Using MI, students will assess readiness for change, help patients identify potential barriers in accordance with patient past pattern of use, and guide them to develop a plan to deal with these barriers

A motivational interviewing intervention customized by patient adherence patterns (NCT03985098) – 03.28.2018

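### The Phase 1 window opens on a fill, so index-fill days' supply fixes the earliest adherence indicators, yet it is not a covariate in the trajectory-predictor models

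*Combined protocol and SAP*

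**What the plan says.** Section 3.1 admits patients "having a prescription filled for an ACEI or ARB medication during the month of January, 2017". Section 9.1 makes that fill time zero: "the first prescription date during this time will be considered the index date". It continues: "Patient adherence will be assessed during the one year following the index date". The assessment is divided as follows: "During each of the 12 consecutive 30-day periods of adherence assessment", each with a binary full-adherence indicator "defined as PDC= 0.8 vs. non-adherence will be created". All twelve go into the logistic trajectory model: "The 12 binary indicators of full adherence will then be modeled during each 30-day period as a longitudinal response".

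Nothing in 9.1 sets aside the days covered by the index fill, and nothing conditions the trajectory model on days' supply.

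The trajectories then have three uses:
- They are the outcome of the logistic models for predictors (8.1 and 9.1).
- They determine which education protocol a patient receives (the customization text after 9.2). That text gives examples of expected patterns: "some patients can have high medication use in the early part of the follow up period but poor after, others may have low initial use".
- They form the randomisation strata (9.3): "Patients will be categorized by their adherence trajectory identified in phase 1 and will be randomized to intervention vs. not within each category".

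Section 6.2 lists days of supply among the pharmacy-file fields. The 9.2 covariate list does not include it.

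**The concern.** PDC counts days supplied. When the window opens on a fill, the first indicators record the size of that fill and say nothing about later refilling. If patients' index fills differ in length, the number of predetermined indicators differs too, and the trajectory model treats them like any other response.

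Two things are at stake. First, in the predictor models for 8.1, index-fill days' supply could influence trajectory membership without being adjusted for, and any listed covariate associated with it could pick up its effect. Second, in the tailoring, two patients who each stop after one fill could be read as different patterns (discontinued at once, or good early and poor later) and start from different scripts.

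**Working it through.** The plan gives no figure to reproduce beyond 12 × 30 = 360 days, which is consistent.

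**Inputs from the documents.** The clock starts on the index fill date, there are twelve 30-day periods, and the threshold is 0.8. The threshold sign in 9.1 is read as at least 0.8. The customization text describes non-adherence as below 0.8, and the Phase 2 dichotomisation in section 20 uses 80% or more. The sign may have been lost in text conversion and is not counted as an error.

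**Assumed inputs.** Index supplies of 30 and 90 days. The documents give no distribution.

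**Supply needed to fix a month.** A month is adherent at 0.8 × 30 = 24 covered days.
- Month 1: 24 days.
- Month 2: 30 + 24 = 54 days.
- Month 3: 60 + 24 = 84 days.

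If counting starts the day after the index date, each figure rises by one (25, 55, 85). A fill of 23 days or less fixes nothing.

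**Resulting codes, twelve periods as written:**

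| Pattern | 30-day fills | 90-day fills |
|---|---|---|
| One fill, no refill | 100000000000 (PDC 30/360 = 0.083) | 111000000000 (PDC 90/360 = 0.250) |
| Refills on run-out, no fill after day 45 | 110000000000 | 111000000000 |
| Refills on run-out, no fill after day 100 | 111100000000 (120/360 = 0.333) | 111111000000 (180/360 = 0.500) |
| 15-day delay at every refill | 100100100100 (240/360 = 0.667) | 111011011101 (315/360 = 0.875) |
| 100-day gap after index supply, then continuous | 100001111111 | 111000011111 |

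A 30-day filler who refills twice and stops is also 111000000000, the same as a 90-day filler who never refills.

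The third and fourth rows show that package size also acts at later refills. A 90-day refill on day 91 fixes months 4 to 6 in the same way.

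**Illustration only.** The behaviour mix and 90-day shares here are assumptions. The simulation used 4,000 patients, the same refill behaviour in both fill sizes, 90-day shares of 20%, 50% and 80%, and a four-group cubic logistic trajectory model.
- Month 1 was 1.00 for everyone.
- Months 2 and 3 were 1.00 in 90-day fillers, against 0.76 and 0.73 in 30-day fillers.
- Intermittent refillers fell in the intermittent trajectory in 95–96% of 30-day and 28–59% of 90-day patients.
- Stoppers fell in the early-stop trajectory in 70–73% and 51–57% respectively.

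These gaps combine the index-fill effect with the later-refill effect, so they show direction and not the size of the index-fill part.

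**Check of the obvious remedy.** Restart the clock after the index supply and model nine periods (days 31–300 for 30-day fillers, days 91–360 for 90-day fillers).

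| Pattern | As written | After restart |
|---|---|---|
| Supply ends day 180 (6 × 30 or 2 × 90) | 111111000000 for both | 111110000 vs 111000000 |
| Covered to day 90, gap to day 210, then continuous | 111000011111 for both | 110000111 vs 000011111 |
| 30-day filler, supply ends day 300 | 111111111100 | 111111111, as if fully adherent |
| 15-day delay at every refill | 100100100100 vs 111011011101 | 001001001 vs 011011101 |

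The restart does align one-fill stoppers (000000000 for both). It also gives equal coverage different codes, hides stopping in months 11–12, and leaves the delay pattern unaligned.

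**The case against.** The best defence is that PDC measures days covered. One 90-day fill and three 30-day fills both cover 90 days, so giving them the same code is what the measure is meant to do. On that view the patients in the first table row did not behave alike. This stands as a reason to keep the twelve periods from the index date as the main model. It does not answer the predictor question: the early indicators still depend on a baseline quantity that is on file and not in the models.

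Other points also stand:
- Month 1 is nearly constant, so alone it hardly separates groups. The separation comes from months 2–3 and from later refills.
- Regimen complexity, baseline PDC and prevalent or incident use are already covariates. Regimen complexity is not defined, so it cannot be assumed to carry days' supply.
- The scripts are not yet written, and students explore barriers with the patient during the call (9.3). The trajectory code is a starting point.

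A reader might infer more than the documents support:
- **That every non-adherent curve has a built-in early fall.** A patient covered to day 180 shows none.
- **That all patients can record non-adherence from month 4.** A 90-day refill fixes later months too.
- **That a low-initial-use pattern is impossible.** It can still appear from month 2 or month 4, and the plan offers it only as an example.

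**Conclusion.** The point holds in a limited form. It follows from the definitions alone that an index supply of at least 24 days fixes month 1 and one of at least 84 days fixes months 1–3 (25 and 85 if counting starts the next day). Trajectory membership can therefore partly reflect index-fill days' supply. That affects the interpretation of the trajectories, the predictor results and the choice of script.

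How much it matters depends on the mix of days' supply among index fills, which the documents do not give. If nearly all index fills had the same length, the distortion between patients at the start of the window would be small.

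A reader might also infer that the Phase 2 comparison is biased. It is not: trajectory is fixed before randomisation, and randomising within an imperfect category is still valid.

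**What to change.** 1. In 9.2, add index-fill days' supply to the covariates for the trajectory-predictor models.
2. In 9.1, keep the twelve periods from the index date as the main model. Add one sensitivity analysis that refits it with months lying wholly inside the index fill set to missing, and report how many patients change trajectory before the scripts are finalised. State whether the index day is day 1: under a next-day start, a 30-day fill covers only 29 of the 30 days of month 1, so the missing-month rule must be worded to match.
3. Do not restart the clock with nine periods, for the reasons shown in the working.

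The cost is one covariate and one further model fit, using a field already in the pharmacy file (6.2). Two limits remain. The covariate adjusts the predictor models but leaves trajectory assignment unchanged. Neither step removes package-size effects at later refills, and the report should say so.

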4.0 Vulnerable Populations

4.1 N/A

5.0 Number of Subjects

- 5.1 This study will have two phases. In the retrospective analysis stage, Cigna Healthspring will provide data on patients who fulfill eligibility criteria mentioned above. It is expected that this data will have approximately 22,000 patients with DM and HTN.
- 5.2 In the intervention phase, 250-300 patients will be included in the intervention phase. If 1 control is used for each patient in the intervention group, the total sample of phase 2 is expected to be 500-600.

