8.0 Study Endpoints

- 8.1 Develop group-based trajectory models to identify patients with similar medication filling behavior patterns among patients utilizing ACEI/ARBs with co-morbid HTN and DM enrolled in a MAP and examine predictors associated with having different trajectories.
- 8.2 Customize a pharmacy student telephone intervention incorporating MI by patient adherence behavior patterns identified under aim 1.
- 8.3 Demonstrate the benefit of the customized intervention on ACEI/ARB adherence among non-adherent patients with co-morbid HTN and DM enrolled in a MAP.

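### Predictors of trajectory are to be found by regressing on the assigned label with no allowance for classification error, which can bias odds ratios unless the trajectories separate well

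*Combined protocol and SAP*

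**What the plan says.** The second half of endpoint 8.1 (section 8.0) is to "examine predictors associated with having different trajectories". Section 9.1 gives the method in three steps.

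- A logistic group-based trajectory model: "The 12 binary indicators of full adherence will then be modeled during each 30-day period as a longitudinal response".
- A classification: "Patients will be assigned to a trajectory on the basis of these models".
- The predictor analysis: "Several logistic regression models will then be carried out to identify predictors associated with specific trajectories for adherence".

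The word *then* in the last quote places the regressions after the assignment. The document mentions no posterior weighting, no covariates in the membership probabilities, no correction for classification error and no threshold for classification quality. It does not state the number of trajectories, the reference trajectory, or whether the regressions are binary or multinomial. On size, section 5.1 says: "It is expected that this data will have approximately 22,000 patients with DM and HTN".

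**The concern.** Trajectory membership is latent. Twelve binary indicators give each patient a set of posterior probabilities, not an observed group. If the most probable group is entered as a known outcome, misassigned patients take their covariates into the wrong group. The odds ratio for one trajectory then absorbs part of the predictor's effect on the trajectories it is confused with, and the standard errors ignore the uncertainty of assignment.

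Some confusion should be expected. The paragraph on customising the intervention foresees patients who start high and fall away, patients who start low and improve, and then: "Some may have intermittent adherence throughout the follow up time, others may simply discontinue". Patterns such as decline and discontinuation may be hard to tell apart on twelve yes/no values.

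At stake is the predictor half of endpoint 8.1: associations could be understated, and some contrasts that are truly null could be reported as findings with narrow intervals.

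**Working it through.** There is no figure in the document to reproduce. No odds ratio, interval, alpha or classification accuracy is given for this analysis, so the check is a simulation.

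**From the document:** n of about 22,000 (section 5.1); 12 monthly binary indicators, assignment, then logistic regression (section 9.1).

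**Assumed:** five groups (adherent, declining, improving, intermittent, discontinuing) with shares 50/14/10/16/10% when the predictor is absent; quadratic logit curves; months independent within a group; one binary predictor with 40% prevalence; the correct number of groups fitted; assignment to the highest posterior; 95% Wald intervals. Each setting had 300 replicates, so the Monte Carlo standard error at 95% coverage is √(0.95 × 0.05 / 300) = 1.3 points.

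**Scenario A: effects differ between trajectories.** True odds ratios against the adherent group are 1.0 / 1.0 / 1.5 / 2.0. Assign-then-regress at n = 22,000 gave:

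| Separation | Average posterior | Misassigned | Mean odds ratios | Coverage (%) |
|---|---|---|---|---|
| High | 0.91–0.99 | 5% | 1.04 / 1.04 / 1.45 / 1.95 | 86 / 89 / 84 / 88 |
| Moderate | 0.72–0.94 | 14% | 1.07 / 1.08 / 1.33 / 1.86 | 62 / 64 / 19 / 56 |
| Low | 0.56–0.89 | 22% | 1.11 / 1.11 / 1.26 / 1.83 | 32 / 56 / 1 / 41 |

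False-positive rates for the two null contrasts were 14% and 11% (high), 38% and 36% (moderate), and 68% and 44% (low).

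**Scenarios where the problem is small or absent.**

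- B, true odds ratios 1.5 / 1.5 / 1.5 / 2.0: coverage 92–97% at high separation (log odds ratio bias at most 3%), 74–90% at moderate (5–10% toward the null), 46–67% at low (13–22% toward the null).
- C, all 1.2, moderate separation: coverage 91–94%.
- D, all 1.0: no bias, and coverage 93–97% at every separation.

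**Dependence on n.** With bias b and standard error SE, coverage is about Φ(1.96 − |b|/SE) − Φ(−1.96 − |b|/SE). Take the first null contrast in scenario A at moderate separation.

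- n = 22,000: b = ln 1.074 = 0.071, SE = 0.044, ratio 1.62, predicted coverage 63% (simulated 62%).
- n = 5,000: b = ln 1.080 = 0.077, SE = 0.092, ratio 0.84, predicted coverage 87% (simulated 85%).

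The bias is essentially unchanged. Only the standard error moves, so more patients make coverage worse. Over all four contrasts, coverage was 70–86% at n = 5,000 and 19–64% at 22,000.

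**Joint model.** With the predictor in the membership probabilities, scenario A at moderate separation gave 1.00 / 1.00 / 1.50 / 2.00. Coverage over all settings at n = 22,000 was 92–99%. Standard errors were 0.054 / 0.074 / 0.054 / 0.046 against 0.044 / 0.052 / 0.039 / 0.042, ratios of 1.23 / 1.42 / 1.38 / 1.10.

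**Agreement under other assumptions.** Two further simulations at n = 22,000 used other groups and curves.

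- Four or five groups, mean posteriors 0.76–0.97, 100 runs: a true log odds ratio of 0 was estimated at 0.05–0.06 with coverage 67–69% (Monte Carlo standard error about 4.7 points). A true 0.30 came out at 0.26 (four groups, coverage 80%) or 0.21 (five groups, 41%).
- Four groups, mean posteriors 0.81–0.96, 40 runs: true 0 / 0.60 / 0.30 came out at 0.05 / 0.57 / 0.26 with coverage about 73–85%; the joint fit gave 0.00 / 0.60 / 0.31.

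**The case against.** The strongest reply is that the size of the error cannot be derived from the document. Separation, group shares and predictor effects are all assumed, and scenarios B (at high separation), C and D show coverage at or near nominal. That stands, and it limits the point to what can happen. It does not remove it, because high separation cannot be presumed before the model is fitted, and a search for what distinguishes trajectories is a search for predictors whose effects differ.

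Four stronger readings might be inferred, and the document supports none of them.

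- *The odds ratios will be biased and the intervals will fail at 22,000.* This depends on separation and effects that are not given. Moreover, 22,000 is an expected data size; section 3.2 applies the eligibility criteria at the analysis stage, so the analysed cohort may be smaller.
- *Irrelevant predictors will be flagged about a third of the time.* That rate applies only to a contrast that is null while the same predictor acts on other trajectories. Scenario D shows no excess for a predictor unrelated to all of them.
- *Running several regressions is itself a source of bias.* With known membership, separate fits against a common reference target the same odds ratios as a multinomial model. One-trajectory-versus-all-others models would target a different odds ratio, but section 9.1 does not specify that form.
- *The trial's main result is at risk.* Customisation rests on the patterns and the team's view of barriers, randomisation uses the label as a stratum, and the outcome analysis in section 20.0 uses none of these odds ratios.

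It is also fair to say that treating the label as error-free is inferred from silence. It is nevertheless the natural reading of the sequence in section 9.1. Finally, the joint model was tested under favourable conditions: one covariate and independent months. Multi-month fills would break that independence and were not simulated.

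**Conclusion.** The concern holds in conditional form. The method as written can give biased log odds ratios and intervals that are too narrow for predictors whose effects differ between trajectories, unless separation is high.

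At moderate separation, contrasts null for one trajectory but not for others had about 60–70% coverage in two of the simulations; the smaller third run, with coverage of about 73–85% over its contrasts, points the same way. Even with 5% misassigned, scenario A coverage was 84–89%. With high separation and similar effects it was 92–97%. All of these figures rest on the assumptions listed above and are illustrations, not predictions for this cohort.

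The consequence is confined to the predictor half of endpoint 8.1. The change is worth making because it improves a stated analysis with data already to be held, but the randomised comparison does not depend on it.

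**What to change.** Replace the predictor sentence in section 9.1 with one that says:

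- predictors will be estimated in a multinomial model with the consistently adherent trajectory as reference;
- classification error will be accounted for, either by a bias-adjusted three-step analysis or by fitting the membership model jointly with the trajectories;
- average posterior probabilities will be reported for each group.

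Keep the assigned label only for the intervention code and the randomisation stratum.

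No new data are needed. The costs are plan wording, more programming, and longer run time with the more than twenty covariates in section 9.2. Standard errors rise by roughly 10–42% in scenario A at moderate separation. The rise can be larger when separation is poor: at low separation in scenario D the ratios were 0.066/0.042 = 1.57, 0.112/0.054 = 2.07, 0.099/0.042 = 2.36 and 0.053/0.048 = 1.10. That width is uncertainty which the assigned-label analysis leaves out. Only the joint model was simulated here; the three-step form was not.

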6.0 Recruitment Methods

LOCAL:

- 6.1 This study will start with the retrospective phase which does not involve recruitment of patients, but involves analysis of existing data. De-identified data will be obtained from Cigna-Healthspring.
- 6.2 The project will be implemented in collaboration with Cigna-Health Spring, a Medicare Advantage Plan in Texas. The health plan has several electronic data files available for analysis including membership file, member

A motivational interviewing intervention customized by patient adherence patterns (NCT03985098) – 03.28.2018

summary file, institutional claims file, professional claims file, quest lab, Cigna-Health Spring's medical claims file (CCMS) and pharmacy file. Pharmacy files contain Part D pharmacy data provided by pharmacy benefits manager including patient/ drug identifying information, fill dates, days of supply, quantity dispensed and dosing for each prescription filled. The refill data will be used to determine the non-adherent patients. ICD-10 codes will be used to determine other exclusions using professional claims data.

Phase 2 will involve project intervention which will be conducted over the phone. A list of actively enrolled members, taking the medication who were a part of phase 1 will be created by Cigna HealthSpring to be used for intervention implementation at their premises. The phone call will be made by University of Houston pharmacy students who will be on rotation at Cigna-HealthSpring. The form of informed consent which will be read to the patient is attached to the IRB. If the patient consents to receive the intervention over the phone, and completes the phone call, the patient forms a part of the intervention group. Five follow-up phones will be attempted one month apart for the patient after the initial call.

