20.0 Data Management

- 20.1 The data which will be provided by Cigna will contain data with encrypted patient IDs. The electronic data files for this study will be processed on a dedicated, layered-security server, which can be accessed only by [name] and designated project staff members who are under the direct supervision of [name]. Since the system is behind multiple firewalls, is monitored regularly, and is accessible only to key personnel, the risk of unlawful penetration is not a significant data safeguard concern. Data will be stored on the secure server for 3 years following the completion of the study. All analysis will be conducted on the desktop at UH College of Pharmacy. The data will not be accessible through any personal computers.

SAS 9.4 is the statistical software, which will be used for the analysis.

A motivational interviewing intervention customized by patient adherence patterns (NCT03985098) – 03.28.2018

Baseline characteristics: Comparisons in baseline characteristics will be made between the 2 study groups (intervention vs. control) using t-tests for continuous variables and chi-square tests for categorical variables. The characteristics evaluated will include predisposing factors: demographics, and number of other medications used; enabling factors: health plan (LIS vs. not), prescriber specialty (specialist vs. primary care); need factors: comorbidities (CHF, MI, CAD, stroke, ESRD, depression), previous hospitalization and CMS risk score.

Baseline PDC in the 12 months prior to intervention and patient past adherence trajectory will also be compared between 2 groups. Because of the randomization, we do not anticipate any significant differences between the two study groups on these characteristics.

Outcome analysis: Refill data during 2 time periods -- 6, and 12 months, following the initial call of the intervention will be evaluated to calculate adherence rates for both the intervention and control groups. The two periods were chosen to evaluate the intervention effect during the 6 months when the follow up calls were ongoing as well as after these calls had stopped. The adherence rate will be defined as proportion of days covered (PDC) for six and twelve month follow up period following the intervention. An intent to treat analysis will be utilized.

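### The Phase 1 predictor regressions include prescriber specialty but make no allowance for patients who share a prescriber, so its confidence interval may be too narrow.

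*Combined protocol and SAP*

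**What the plan says.** Section 8.1 makes it part of the first endpoint to "examine predictors associated with having different trajectories". Section 9.1 gives the method: "Several logistic regression models will then be carried out to identify predictors associated with specific trajectories for adherence". Section 9.2, which follows directly, lists the covariates, including "physician specialty (primary care vs. specialist". Section 20.0 lists the same item among the Phase 2 baseline characteristics and there calls it "prescriber specialty (specialist vs. primary care", which confirms that it describes the prescriber.

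On the data, section 5.1 says "It is expected that this data will have approximately 22,000 patients with DM and HTN". All patients come from one source (section 6.2): "The project will be implemented in collaboration with Cigna-Health Spring, a Medicare Advantage Plan in Texas". The same section describes the pharmacy file as holding "patient/ drug identifying information, fill dates, days of supply, quantity dispensed and dosing for each prescription filled"; a prescriber identifier is not among these fields. On software, section 20.0 says only "SAS 9.4 is the statistical software, which will be used for the analysis". No section mentions clustering, a random effect, generalized estimating equations (GEE) or a robust variance. None gives a number of prescribers, an ICC or a significance level.

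**The concern.** Logistic regression with no variance method named treats each patient as separate evidence on every covariate. For specialty, the independent unit is the prescriber. Patients of one prescriber may also resemble each other in refill pattern, because prescribers influence days supplied, choice of drug class and follow-up. If some of that resemblance remains after adjustment, the model overstates the information on specialty. Chance differences between prescribers' panels could then be reported as a specialty effect. The same applies, to a lesser degree, to other covariates that vary mainly between prescribers, such as drug class.

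At stake is the reliability of one predictor within endpoint 8.1.

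**Working it through.** The plan states no figure for this analysis, so there is nothing to reproduce. The check asks how far the false-positive rate for specialty moves if clustering is ignored.

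**Inputs.** From the documents: specialty is binary and fixed by prescriber (9.2, 20.0), and about 22,000 patients are expected (5.1). Assumed: two-sided 5% level; 20% of prescribers are specialists; the modelled trajectory holds 20% of patients; no true specialty effect; no other covariates; latent-scale ICC of 0.01 or 0.05; an average of *m* = 3 to 20 patients per prescriber, in panels that are equal or skewed (coefficient of variation, CV, of 1).

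**Step 1: put the ICC on the right scale.** The design-effect formula needs the ICC of the observed yes/no outcome, not of the latent logit. The between-prescriber variance is ICC/(1 − ICC) × π²/3, and to first order the observed ICC ρ is *p*(1 − *p*) times that variance.
- Latent 0.05: 0.05/0.95 × 3.29 = 0.173, and 0.16 × 0.173 ≈ 0.028. Numerical evaluation gives about 0.027, which is used below.
- Latent 0.01: 0.01/0.99 × 3.29 = 0.0332, and 0.16 × 0.0332 ≈ 0.0053.

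**Step 2: design effect and false-positive rate.**
DE = 1 + [(1 + CV²)*m* − 1]ρ; false-positive rate = 2[1 − Φ(1.96/√DE)]; the naive interval is too narrow by the factor √DE.

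For latent ICC 0.05 (ρ = 0.027):

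| *m* | DE, equal | Rate | DE, skewed | Rate |
|---|---|---|---|---|
| 5 | 1.108 | 6.3% | 1.243 | 7.9% |
| 10 | 1.243 | 7.9% | 1.513 | 11.1% |
| 20 | 1.513 | 11.1% | 2.053 | 17.1% |

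At *m* = 20 the correct interval is √1.513 = 1.23 times the naive one with equal panels and √2.053 = 1.43 times with skewed panels.

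For latent ICC 0.01 (ρ = 0.0053), *m* = 3 with equal panels gives DE = 1 + 2 × 0.0053 = 1.011 and 5.1%. *m* = 20 with skewed panels gives DE = 1 + 39 × 0.0053 = 1.207 and 7.4%.

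**Step 3: simulation.** With 22,000 patients, a prescriber random intercept and 2,000 runs per setting, the naive Wald test rejected in about 6% to 10% (*m* = 5), 8% to 11% (*m* = 10) and 11% to 19% (*m* = 20) of runs at latent ICC 0.05. At latent ICC 0.01 it was near nominal for panels of 10 or fewer and about 7% at 20. The lower ends match the table. Two upper ends lie above it (10% against 7.9% at *m* = 5, and 19% against 17.1% at *m* = 20), so the upper ends should be read as rough.

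**Step 4: the same data with the fix.** Standard errors clustered on prescriber gave rejection rates of about 4% to 6% in every setting run.

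**The case against.** The strongest reply is that the size of this effect cannot be known from the documents, and that no trial decision turns on it.

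- *The correlation is assumed.* This stands. With one patient per prescriber, or no residual correlation, plain logistic regression is correct.
- *The plan adjusts for much of the mechanism.* Section 9.2 lists drug class, regimen complexity and baseline adherence. This also stands: the relevant ICC is what remains after adjustment, and the figures above have no covariates, so they may be too high.
- *Independence is read from silence, and 9.2 is not tied to one model.* The list includes the trajectory before the intervention, which belongs to Phase 2. But 9.2 follows directly on the Phase 1 regressions, and no other list of Phase 1 predictors exists. Specialty as a Phase 1 predictor is therefore the natural reading, though not an explicit one. Logistic regression run as written, with no variance option, assumes independence.
- *The number modelled may be below 22,000.* Section 3.2 applies the eligibility criteria during the analysis. That could reduce panel sizes, and with them the inflation.

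Three stronger readings are tempting, and the documents support none of them. A reader might infer that the interval is certainly too narrow and the error rate certainly above 5%; that requires an ICC and panel sizes the documents do not give, and even the 5% level is an assumption. A reader might infer that the large sample makes the problem worse; for fixed panel size and ICC, the total does not enter the formula in step 2. A reader might infer that the trial result is undermined; in Phase 2 patients are randomized within trajectory (9.3), and specialty is only a baseline characteristic.

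Applying the design-effect formula directly to a latent ICC also overstates the case. At ICC 0.05 and *m* = 20 with equal panels it gives DE = 1 + 19 × 0.05 = 1.95 and 16.0%, against about 11% on the correct scale.

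**Conclusion.** The point holds as a conditional one. The plan has no method for patients who share a prescriber, although one of its listed predictors is a property of the prescriber. The direction of the error is clear whenever patients share prescribers and residual correlation is positive. Both are plausible within a single health plan, but neither is documented. Over the values examined, the effect runs from negligible to a false-positive rate in the high teens, before any reduction from the planned covariates. It is confined to the predictor part of endpoint 8.1. This is a cheap improvement to the analysis wording, not an error in any figure of the plan.

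**What to change.** In section 9.1, keep the same logistic models and covariates, and state that standard errors will be clustered on the prescriber to whom the specialty field is attributed. In SAS 9.4 this can be done with PROC SURVEYLOGISTIC and a CLUSTER statement, or with GEE under an independence working correlation. State how that prescriber is chosen when a patient has more than one; the plan does not say.

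In sections 6.2, 9.2 and 20.0, ask the health plan to supply an encrypted prescriber ID with the specialty field. This is best settled before the extract is made: the university receives only de-identified data, and without the ID the correction cannot be made from the delivered file.

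The cost is one sentence of analysis text, one added data field, and somewhat wider intervals for specialty and related covariates if clustering is present. If it is not, the results will barely change. No patients or procedures are added.
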